5.3.5.2 Criteria for discontinuing in the case of individual patients

Patients may withdraw from the entire trial including follow-up at any time without penalty and for any reason without prejudice to his or her future medical care.

The following criteria must lead to discontinuation from the clinical trial in individual patients:

- Patient withdraws informed consent

- Pregnancy (see section 7.4)
- Severe protocol violations that result in a significant risk to the patient's safety
- Emergence of the following AEs including:
 - a) Patient reports symptoms which are considered unacceptable by the patient or the Investigator or if any serious AE occurs that is judged as at least possibly related to the IMP by the Investigator
 - b) Abnormal laboratory value(s) confirmed by repeat measurements:
 - Elevated liver transaminases (AST/ALT) $\geq 3 \times$ ULN AND elevated bilirubin total bilirubin $\geq 2 \times$ ULN
 - Elevated serum creatinine $\geq 2 \times$ ULN

The following criteria may lead to discontinuation from the clinical trial in individual patients:

- Use of prohibited concomitant medication as defined in section 5.4.5.

In all cases, the reason(s) for withdrawal, and the primary reason, must be recorded on the electronic data capture (EDC) system / electronic case report form (eCRF). If a patient is prematurely withdrawn from the IMP for any reason, the Investigator must make every effort to perform the evaluations described for the End of Treatment and Follow-up Visits. The Investigator should contact the Medical Monitor, whenever possible, to approve withdrawal of patients in advance.

If a patient withdraws consent and still agrees to undergo a final examination, it will be documented on the eCRF and the patient record.

A patient may also be withdrawn from the IMP by the Sponsor, Regulatory Authorities, or Independent Ethics Committees (IECs) / Institutional Review Boards (IRBs).

Patients who are withdrawn from the trial will be not replaced.

Protocol violation, failure to comply with the trial stipulations/poor compliance may lead to discontinuation from the clinical trial in individual patients.

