5.4.5 Prior and concomitant therapy

Any medication the patient takes other than the IMP, including herbal and other non-traditional remedies, is considered a concomitant medication. All concomitant medications taken in the 6 weeks before the first dose must be recorded in the eCRF. The following information must be recorded in the eCRF for each concomitant medication: brand name, route of administration, start date, stop date, dosage, and indication. Any changes in the dosage or regimen of a concomitant medication must be recorded in the eCRF.

At Screening, patients will be asked which psoriatic treatment they have previously taken (last 6 weeks) and which other concomitant medications they have taken in the last 6 weeks. At each subsequent trial visit, patients will be asked which concomitant medications they are currently taking and have taken since the previous site visit.

For a detailed list of forbidden medication see exclusion criterion 14.

Medication allowed during the course of the trial:

- Topical moisturizers or emollients, UVA/UVB sunscreens, shampoos for scalp psoriasis (without tar), as needed.
- Contraceptives (see section 3.2)
- Any concomitant medication to treat stable diseases (such as well-controlled hypertension, hyperlipidemia, etc.)

Prohibited medication:

- All treatment as specified in exclusion criteria.

Concomitant medications should be kept to a minimum during the clinical trial. However, if these are considered necessary for the patient's welfare and are unlikely to interfere with the clinical trial objectives, they may be allowed at the discretion of the investigator. For a detailed list of forbidden medication see exclusion criterion 14.

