3.3 Analysis populations

3.3.1 Efficacy populations

Intent-To-Treat (ITT)

The full-analysis-set (FAS) will include all randomized patient who received at least one dose of IMP, and had at least one post-baseline assessment. The intention-to-treat (ITT) analysis will be based on the FAS. The FAS is considered primary analysis set for the efficacy analysis.

Per-Protocol (PP)

The valid-cases-set (VCS) will include all patients from the FAS, who completed the assessments of the co-primary endpoints without any protocol violation interfering with the precise evaluation of treatment efficacy and with sufficient exposure to IMP, i.e.

- who completed the visit 5 (Day 84) assessments of PASI and PGA;
- who did not take any prohibited concomitant medications up to the visit 5 (Day 84).

During the blind data review meeting (BDRM) concomitant medications will be reviewed considering timing, duration of concomitant treatment, and influence on the efficacy assessments to determine prohibited medication usage that warrants exclusion from the VCS;

- who were compliant with the dosing regimen. A subject will be considered compliant, if the subject administered $\geq 80\%$ of the planned capsules.

Subjects who prematurely discontinue the treatment due to an adverse event at least possibly related to IMP will not be excluded from the VCS.

Prior to breaking the blind, other additional criteria may be added to the list to accommodate for unforeseen events that occurred during the conduct of the trial that result in noteworthy study protocol violations.

The per-protocol (PP) analysis will be based on the VCS. Primary efficacy endpoints will be evaluated on VCS to assess the sensitivity.

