3.5.1 Missing data

A description of missing data will be provided in the clinical study report.

For the evaluation of success rates of the primary efficacy variables PASI and PGA missing PGA assessments and/or any parts of the PASI assessments will be evaluated as failure to achieve improvement.

For descriptive analyses of PASI, PGA and BSA the last observation carried forward (LOCF) principle will be applied to impute the missing assessments, up to the Day 84 visit. Follow-up assessments will not be imputed.

Sensitivity of the primary efficacy analyses will be evaluated applying PP analyses.

Regarding incomplete recordings for adverse events the following rules apply:

- For start and stop dates no imputation will be applied. If any, start or stop date, is not complete, but required for the classification, i.e. the occurrence of the AE is not explicitly reported as occurring prior first dose (see eCRF), the AE will be considered treatment emergent.
- Missing assessments of severity, intensity and causal relationship to the IMP will be reported as a separate category.

For the determination of the number of years from start of psoriasis to the screening visit missing starting days will be imputed by the first day of month and missing months will be imputed by the first month (January) of the year.

For concomitant therapies (see section 3.2.2.4) incomplete dates will not be imputed. If an incomplete start or stop date does not allow for the classification as prior and/or concomitant therapy - despite of information in eCRF if taken/used prior to first dosing and/or if ongoing at first dosing - the treatment will be reported as prior and as concomitant therapy.

Pharmacokinetic data below LLQ will be replaced as described in 3.4.7.3 for descriptive statistics and for the derivation of $AUC_{(0,t)}$. Missing pre-dose levels will be imputed by zero. Missing intermediate samples, i.e. missing values in between non-missing levels (quantifiable or substituted by LLQ/2) will be imputed by linear interpolation between the last preceding and the next following available value. The last value will be imputed by LLQ/2, if missing.

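### In the primary FAS analysis a Day 84 response reached on prohibited antipsoriatic medication counts as success, and no planned FAS analysis scores it otherwise

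*SAP*

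**What the plan says.** - **Analysis set.** SAP 3.3.1: "The FAS is considered primary analysis set for the efficacy analysis". It takes randomised patients "who received at least one dose of IMP, and had at least one post-baseline assessment". Medication use is not a condition.
- **Response.** SAP 3.4.6.2 defines both co-primary responses by change from baseline at Day 84, with no reference to other treatment.
- **Imposed failure.** SAP 3.5.1 (and Protocol 6.6): "missing PGA assessments and/or any parts of the PASI assessments will be evaluated as failure to achieve improvement". No other rule in either document forces non-response.
- **Prohibited medication in the analysis.** It appears only in the VCS definition, which keeps patients "who did not take any prohibited concomitant medications up to the visit 5 (Day 84". A blind data review looks at timing, duration and influence on efficacy assessments "to determine prohibited medication usage that warrants exclusion from the VCS".
- **Prohibited medication in conduct.** Protocol 5.4.5 prohibits "All treatment as specified in exclusion criteria", and Table 2 there includes topical and systemic psoriasis treatments. In Protocol 5.3.5.2, "Use of prohibited concomitant medication as defined in section 5.4.5" stands under the lead-in "The following criteria may lead to discontinuation from the clinical trial in individual patients", so withdrawal is optional.
- **Withdrawn patients.** Protocol 5.5.1 repeats the Visit 5 procedures, PASI and PGA included, at the Early Termination Visit. SAP 3.5.2 and 3.5.3 assign efficacy assessments made at withdrawal to a planned visit.
- **Sensitivity.** SAP 3.5.1 plans only the per-protocol analysis.

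**The concern.** The plan recognises that other antipsoriatic treatment can distort the efficacy assessments, because it sets up a blinded review to find it. The result of that review never reaches the primary analysis set. In the FAS, a user with a Day 84 value is counted as the score falls, whatever produced the improvement. The PGA endpoint is the more exposed of the two, since one point on a seven-point scale is enough.

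The VCS does not fill the gap. It takes users out of both numerator and denominator, so it conditions on a post-randomisation event. It also drops patients without Day 84 assessments and those below 80% dosing compliance. If VCS and FAS results differ, the reader cannot tell which exclusion is responsible. What is at stake is whether the reported response rates and odds ratios describe the study drug or the study drug plus whatever else was taken.

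**Working it through.** **1. How a user is scored.**

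| Prohibited antipsoriatic use before Day 84, and then | Day 84 value | FAS score |
|---|---|---|
| stays in the trial | observed | as observed |
| withdraws, assessed nearer Day 84 than Day 56, Day 84 visit missing | mapped to Day 84 (SAP 3.5.2, 3.5.3) | as mapped |
| withdraws earlier | missing | failure under SAP 3.5.1 |

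The midpoint of Days 56 and 84 is (56 + 84)/2 = Day 70. On a nearest-visit reading, an assessment after Day 70 fills an empty Day 84 slot. So does one on Day 70 itself if Day 56 is also missing, because ties go to the later visit. The last row is also unsettled. The shells for the responder tables (14.3.3 for PASI 75, 14.3.15 for PGA improvement) are labelled LOCF, and LOCF in SAP 3.1 would carry an earlier value to Day 84 instead of scoring failure.

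**2. The plan's own figure.** SAP 2.2 gives 0.674 against 0.40, 40 per group, two-sided alpha 0.10 and 80% power with a two-group chi-square test. With pooled null variance and no continuity correction:

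power = Φ[(|pA − pP| − 1.645·s0)/s1], where s0 = √(2p̄(1 − p̄)/n) and s1 = √(pP(1 − pP)/n + pA(1 − pA)/n).

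Here p̄ = 0.537, s0 = 0.1115 and s1 = 0.1072. (0.274 − 1.645 × 0.1115)/0.1072 = 0.845, so power is 0.801. The stated figure reproduces.

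**3. Illustration.** Neither document gives a rate of prohibited use. Assume that a share u of an arm uses it, that all of them would otherwise fail, that all have a Day 84 value, and that a share q then respond. The arm's rate becomes p + u·q. For 10% placebo and 5% active use with q = 0.5:

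- placebo: 0.40 + 0.10 × 0.5 = 0.450
- active: 0.674 + 0.05 × 0.5 = 0.699
- difference: 0.249
- power at 40 per arm: s0 = 0.1106, s1 = 0.1070; (0.249 − 1.645 × 0.1106)/0.1070 = 0.627, giving 0.73

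The range by the same formula, at 40 per arm (the evaluable number) and 50 per arm (150 recruited over three arms, which the FAS could approach):

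| Use, placebo / active | q | Placebo | Active | Difference | Power, n = 40 | Power, n = 50 |
|---|---|---|---|---|---|---|
| none | – | 0.400 | 0.674 | 0.274 | 0.80 | 0.87 |
| 5% / 2% | 0.5 | 0.425 | 0.684 | 0.259 | 0.76 | 0.84 |
| 10% / 5% | 0.5 | 0.450 | 0.699 | 0.249 | 0.73 | 0.82 |
| 15% / 5% | 0.75 | 0.5125 | 0.7115 | 0.199 | 0.57 | 0.66 |
| 10% / 10% | 0.5 | 0.450 | 0.724 | 0.274 | 0.81 | 0.88 |
| 5% / 10% | 0.5 | 0.425 | 0.724 | 0.299 | 0.87 | 0.93 |

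The last row is the reverse case: its gain in apparent power is an inflated difference, not a benefit. The n = 50 column keeps the planning rates and does not model dropouts scored as failures.

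**The case against.** - **The observed outcome is a legitimate target.** Scoring Day 84 values regardless of other therapy is an accepted intention-to-treat approach. This stands, and it is why the point does not ask for the primary rule to be replaced. It does not explain why no alternative is shown in the same population.
- **The consequence is limited and partly visible.** The trial is exploratory, with no formal hypotheses and descriptive p-values. Table 14.1.4 counts VCS exclusions for interfering medication by arm, and Table 14.2.23 lists concomitant therapies by arm. This lowers the weight of the point. However, Table 14.1.4 counts only the primary reason per patient, and neither table shows how the response rates would change.
- **The remedy still rests on judgement.** The blind data review decides case by case. That is true, but it is blinded and already planned.

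Three stronger readings are tempting, and the documents do not support them. A reader might infer that withdrawal guarantees failure, so that two patients with the same medication history always get opposite scores. The mapping rules and the LOCF labels contradict that. A reader might infer dilution, on the view that placebo patients will use more. Neither document says so, and no rescue treatment is defined. A reader might also infer that the primary analysis falls below 80% power. At 50 per arm, the 10%/5% case still gives 0.82.

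**Conclusion.** The gap is real on the text of both documents. In the primary analysis, use of prohibited antipsoriatic medication does not affect scoring once a Day 84 value exists, and the one sensitivity analysis deletes users instead of counting them.

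Its direction and size cannot be derived from the documents. Under the assumed 10%/5% use, with users who would otherwise fail and half of them responding, the difference drops by 0.025, from 0.274 to 0.249. Power goes from 0.80 to 0.73 at 40 per arm, or from 0.87 to 0.82 at 50. Equal use leaves the difference unchanged, and heavier active use would exaggerate it. These powers are for the plan's unstratified chi-square test, not the centre-stratified CMH test that will be run. Given the exploratory purpose, this is an inexpensive improvement to make before unblinding, not a defect that undermines the trial.

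**What to change.** 1. In SAP 3.5.1, add an FAS sensitivity analysis of PASI 75 and PGA improvement at Day 84. Score as non-responder every patient whom the blind data review classes as having used interfering prohibited antipsoriatic medication before Day 84. Use the same CMH analysis and show it beside the observed-value primary analysis.
2. Record that classification for all FAS patients before the blind is broken, separately from other reasons for VCS exclusion.
3. Reconcile the missing-equals-failure rule in SAP 3.5.1 with the visit mapping in SAP 3.5.2 and 3.5.3. State whether an early-termination assessment may fill Day 84 in the responder analysis. Correct either the rule or the LOCF labels on the responder tables (14.3.3 and 14.3.15, and their VCS counterparts 14.3.9 and 14.3.18).

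The cost is SAP wording and one more table per co-primary endpoint, since the medication review is already planned. The added analysis estimates something different, namely response without other antipsoriatic therapy, and should be labelled so. If the planning rates already exclude medication-driven response, it restores the planned contrast of 0.274 with power 0.80 at 40 per arm. Nothing here changes which medication is prohibited or when patients are withdrawn.

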3.3.2 Safety populations

Safety-evaluation-set (SES)

The safety-evaluation-set (SES) will include all patients who received any trial medication at least once; all safety analyses will be based on the SES.

Pharmacokinetic-evaluation-set (PKS)

All subjects without any protocol deviations that could interfere with the administration of the treatment or the evaluation of systemic concentrations of MP1032, who received at least one dose of IMP and who have any completed determination of MP1032 levels will be included in the pharmacokinetic-evaluation-set (PKS).

3.4 Statistical methods

Statistical analyses will be performed using two-sided tests, without adjustment for multiplicity. All p-values will be interpreted descriptively.

Data will be summarized by treatment group (and by visit when applicable), with respect to demographic and baseline characteristics, efficacy variables, and safety variables.

Summary statistics will include the mean, number of non-missing cases (n), standard deviation, median, minimum, and maximum values for continuous variables, and frequencies and percentages for categorical variables.

Categorical efficacy variables will be analyzed using the Cochran-Mantel-Haenszel (CMH) test with stratification by (pooled) analysis center and the Fisher's exact test in case of analyses without stratification (mainly for safety assessment).

Selected scores will be analyzed using an analysis of covariance (ANCOVA) model, with treatment group and (pooled) analysis center as factors and baseline outcome as covariate.

Time to event data will be analyzed using the Kaplan-Meier method, and treatment group differences will be tested by the log-rank test.

3.4.1 Demographics and baseline characteristics

Demographic data (age, sex, race) and background data (height, weight, BMI, years of psoriasis), including smoking and alcohol consumption, will be summarized using descriptive statistical methods by treatment group for the ITT, Safety, and PP populations. Years of psoriasis at screening visit will be determined with one decimal (see section 3.5.1).

3.4.2 Discontinuations and dropouts

Subjects discontinuing the study will be listed in the clinical study report with reason for discontinuation and last study day given.

A summary will be presented for the reason for discontinuation from the trial and for discontinuation from the treatment phase, i.e. discontinuation prior to Day 84/Week 12 visit.

3.4.3 Current medical conditions

Relevant medical history of the past five years and psoriasis history will be assessed at screening and will be classified on the basis of the Medical Dictionary for Regulatory Activities (MedDRA) (see section 3.5). Current medical conditions, i.e. medical conditions ongoing at first dosing, will be presented by system organ class (SOC) and preferred term (PT) for each treatment group in the FAS. In any given category (e.g., SOC) a subject will be counted only once. Descriptive summaries of subject's years of psoriasis will be presented (see section 3.4.1).

3.4.4 Prior and concomitant therapies

All concomitant medications, therapies and procedures taken in the 6 weeks before the first dose are collected. Previous and concomitant therapies (drug treatments and non-drug therapies) will be classified on the basis of the WHO Drug Dictionary Enhanced (see section 3.5). Medical procedures will be classified on the basis of MedDRA (see section 3.5).

Previous and concomitant therapies will be presented by WHO-drug Level 3 ATC categories (therapeutic/pharmacological subgroup) and preferred term for each treatment group in the FAS. In any given category (e.g., drug category) a subject will be counted only once.

Concomitant medical procedures will be listed with MedDRA SOC and PT.

3.4.5 Compliance

The % treatment compliance will be determined as the number of performed treatment applications in relation to the planned applications within the individual subjects treatment phase:

- total number of applications =
planned applications – # missed applications + # overdose applications
- % treatment compliance =
100 * total number of applications / # planned applications

The % dosing compliance will be determined as the number of dosed capsules in relation to the number of planned capsules within the individual subjects treatment phase:

- total number of dosed capsules =
$$6 * \# \text{ planned applications} - \# \text{ missed capsules} + \# \text{ overdose capsules}$$
- % dosing compliance =
$$100 * \text{total number of dosed capsules} / (6 * \# \text{ planned applications})$$

The % treatment compliance and % dosing compliance will be summarized by descriptive statistics and frequency counts will be given for sufficient ($\geq 80\%$) and insufficient ($< 80\%$) compliance.

3.4.6 Efficacy analyses

3.4.6.1 Hypotheses

Since this is an exploratory trial no formal hypotheses are postulated. The data will be evaluated descriptively.

3.4.6.2 Statistical analyses

Primary efficacy endpoints

The co-primary endpoint response in PASI 75 at Week 12 (Day 84) is defined as 75% improvement in PASI score compared to baseline (i.e. percent of change from baseline $\leq 75\%$). The co-primary endpoint improvement in PGA at Week 12 (Day 84) is defined as reduction by 1 or more points on the PGA scale in comparison to baseline.

The comparisons of the treatment groups MP1032 300 mg bid and MP1032 150 mg bid, each vs. the placebo treatment, with respect to each, the PASI 75 rate and PGA improvement rate, at Week 12 (Day 84) will be evaluated by the CMH test stratified by (pooled) analysis center. The common odds-ratio with 95% confidence interval will be provided. The homogeneity of the individual odds-ratios will be assessed by the Breslow-Day test.

Secondary efficacy endpoints

Secondary efficacy endpoints will be evaluated descriptively. The methodology outlined at the top of this section 3.4.6.2 will be applied for pairwise treatment comparisons vs. placebo:

The PASI 50 responder rate at Week 12 (Day 84) will be evaluated according to the primary efficacy endpoints, as well as the PASI 75, PASI 50 and PGA improvement at Week 4 (Day 28) and Week 8 (Day 56) of the treatment phase and at follow-up, 4 weeks after end of treatment.

The change in the PASI score from baseline to each post baseline visit, respectively, will be evaluated using an analysis of covariance (ANCOVA) model, with treatment group and (pooled) analysis center as factors and baseline outcome as covariate, in both analysis sets, FAS and VCS.

The time to achievement of PASI 50 and PASI 75, respectively, will be evaluated using the Kaplan-Meier method. The study day of first achievement of PASI 50 and PASI 75, respectively, will be the considered event, with study day of last assessment as the time point of censoring, in case of no occurrences of PASI 50 or PASI 75. Pairwise treatment group differences will be tested by the log-rank test.

Location shift in change from baseline in PGA will be assessed using Hodges-Lehmann Estimation with comparison by the Wilcoxon rank sum test, in both analysis sets, FAS and VCS.

Descriptive summaries will be provided for each parameter by treatment group and by visit, if applicable. Percentages will be provided based on the number of non-missing cases, if not otherwise stated. For PASI and PGA the descriptive summaries will be performed in both analysis sets, FAS and VCS.

Subgroup analyses

The following subgroups, based on baseline parameter, will be evaluated with respect to the primary efficacy variables PASI and PGA for each post-baseline visit within the FAS:

Table 4 Subgroups

Center:	• Analysis (pooled) centers		
Age:	• 18 to 40	• >40	
Sex:	• Male	• Female	
BMI:	• ≤ 24.9 (normal)	• 25.0 - 29.9 (pre-obesity)	• ≥ 30.0 (obesity)
Years of psoriasis:	• 1 to 10	• >10	
Smoking	• Current	• Never or former	
Cigarette smoking:	• <1 to 10	• >10	
PGA:	• 3 to 4	• 5 to 6	
PASI:	• ≤ 15	• > 15	
CRP:	• <10 mg/dl	• ≥ 10 mg/dl	

The change in PASI and PGA will be evaluated utilizing following analyses:

- mean change from baseline in PASI by ANCOVA model
- location shift in change from baseline in PGA by Wilcoxon rank sum test and Hodges-Lehmann Estimation

If applicable, the analyses will be stratified by country.

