3.1 Definitions

The following definitions apply:

- Baseline: The latest non-missing observation prior to first treatment with IMP.

Baseline data definition	obtained on/at
Age, race, height, body weight, BMI	Screening
Relevant medical history (last 5 years) including psoriasis history, relevant surgical history (last 5 years) and relevant previous medication (last 6 weeks) including psoriatic treatment taken (last 6 weeks)	Screening
Smoking and alcohol consumption	Screening
Concomitant medication	Day 1
Adverse events	Day 1
Physical examination	Day 1, Screening*
Vital signs (blood pressure, pulse rate)	Day 1, Screening*
Safety laboratory parameters	Day 1, Screening*
PASI, PGA, BSA	Day 1, Screening*

*only in case of missing Day 1 assessment

- Change from baseline = post baseline value – baseline value
- Percent change from baseline = $100 * \text{change from baseline} / \text{baseline value}$
- Last observation carried forward (LOCF): The last observed value (either scheduled or unscheduled) carried forward and used for all directly subsequent and missing scheduled points.
- Current medical conditions – medical conditions ongoing at first dosing.
- Prior therapy: Any medication or therapy taken prior to start of first IMP dosing.
- Concomitant therapy: A medication or therapy ongoing at start of first IMP dosing, or starting after the first IMP dosing.
- Treatment emergent adverse event (TEAE): Adverse event with an onset (or worsening) on or after the time of the first IMP dosing.
- Time to achievement of PASI 50 (75): Day of first visit were PASI 50 (75) is observed.
- Analysis centers: Pooled small centers for analyses, as described in section 3.5.4.

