3.2 Analysis variables

3.2.1 Efficacy variable(s)

3.2.1.1 Psoriasis Area Severity Index (PASI)

The PASI quantifies the severity and extent of the disease and weighs these with the body surface area involvement. It involves the assessment of erythema (E), infiltration (I),

desquamation (D), and body surface area involvement (A) over 4 body regions: head (h), trunk (t), upper (u) and lower extremities (l).

Degree of severity (for E, I, D) per body region	Value given
No symptoms	0
Slight	1
Moderate	2
Marked	3
Very marked	4

Surface involved (A), per body region	Value given
<10%	1
10-29%	2
30-49%	3
50-69%	4
70-89%	5
90-100%	6

Because the head (h), upper extremities (u), trunk (t), and lower extremities (l) correspond to approximately 10%, 20%, 30%, and 40% of body surface area, respectively, the PASI score is calculated by the formula:

$$\text{PASI} = 0.1*(\text{Eh} + \text{Ih} + \text{Dh})*\text{Ah} + 0.2*(\text{Eu} + \text{Iu} + \text{Du})*\text{Au} + 0.3*(\text{Et} + \text{It} + \text{Dt})*\text{At} + 0.4*(\text{Ei} + \text{Ii} + \text{Di})*\text{Al}$$

The PASI score ranges from 0 to 72, with a higher score indicating increased disease severity and will be assessed at the time points specified in Table 2.

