3.2.1.4 Primary efficacy variable(s)

The primary efficacy variables are:

1. 75% improvement (response) in their PASI score (PASI 75) and
2. Improvement (1 or more points on a 7 point scale) in their PGA score

The secondary efficacy variables are:

3. 50% improvement (response) in their PASI score (PASI 50)
4. Mean PASI score and change to baseline
5. Time to achieve PASI 50 and PASI 75
6. Mean score and change from baseline in the PGA
7. Mean score and change from baseline in the BSA
8. PK data

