Mean ± SD	XX.X ± XX.X	XX.X ± XX.X	XX.X ± XX.X
Median	XX.X	XX.X	XX.X
Min , max	XX.X , XX.X	XX.X , XX.X	XX.X , XX.X
Change from Baseline ¹			
N	XX	XX	XX
Mean ± SD	XX.X ± XX.X	XX.X ± XX.X	XX.X ± XX.X
Median	XX.X	XX.X	XX.X
Min , max	XX.X , XX.X	XX.X , XX.X	XX.X , XX.X
Week 16 / Follow-up			
N	XX	XX	XX
Mean ± SD	XX.X ± XX.X	XX.X ± XX.X	XX.X ± XX.X
Median	XX.X	XX.X	XX.X
Min , max	XX.X , XX.X	XX.X , XX.X	XX.X , XX.X
Change from Baseline ¹			
N	XX	XX	XX
Mean ± SD	XX.X ± XX.X	XX.X ± XX.X	XX.X ± XX.X
Median	XX.X	XX.X	XX.X
Min , max	XX.X , XX.X	XX.X , XX.X	XX.X , XX.X

¹ Baseline: Last observation collected prior to first dose of any IMP, i.e. Day 1 assessment or, if missing, Screening assessment.

Source data: <DATASET> <DATE>
Program: <SAS PROGRAM> <DATE>

Figure 14.1: PASI – Lineplot: Mean values by treatment over time – LOCF (FAS)
Mean values per visit and treatment (visits on x-axis)

Figure 14.2: PASI – Lineplot: Mean change from baseline by treatment over time – LOCF (FAS)
Mean change from baseline per visit and treatment (visits on x-axis)

Table 14.3.3: PASI – PASI 75 responders – LOCF (FAS)
(Part 1 of 2)

PASI 75¹ – LOCF	MP1032 300 mg bid (N = XX)	MP1032 150 mg bid (N = XX)	Placebo bid (N = XX)
Week 4			
N	XX	XX	XX
Responder	XX (XXX.X%)	XX (XXX.X%)	XX (XXX.X%)
Non responder	XX (XXX X%)	XX (XXX X%)	XX (XXX X%)
Comparison vs Placebo ²			
p-value	X.XXX	X.XXX	--
Odds ratio	X.XX	X.XX	--
Confidence interval	X.XX, X.XX	X.XXX	--
Breslow-Day test ³	X.XXX	X.XXX	--
Week 8			
N	XX	XX	XX
Responder	XX (XXX.X%)	XX (XXX.X%)	XX (XXX.X%)
Non-responder	XX (XXX.X%)	XX (XXX.X%)	XX (XXX.X%)
Comparison vs Placebo ²			
p-value	X.XXX	X.XXX	--
Odds ratio	X.XX	X.XX	--
Confidence interval	X.XX, X.XX	X.XXX	--
Breslow-Day test ³	X.XXX	X.XXX	--
Week 12 / EoT			
N	XX	XX	XX
Responder	XX (XXX.X%)	XX (XXX.X%)	XX (XXX.X%)
Non-responder	XX (XXX.X%)	XX (XXX.X%)	XX (XXX.X%)
Comparison vs Placebo ²			
p-value	X.XXX	X.XXX	--
Odds ratio	X.XX	X.XX	--
Confidence interval	X.XX, X.XX	X.XXX	--
Breslow-Day test ³	X.XXX	X.XXX	--

¹ 75% improvement in PASI score

² Cochran-Mantel-Haenszel (CMH) test: p-value for the hypothesis, that all within-stratum odds ratios equal to 1 and estimate of the common odds ratio with 95% confidence interval

³ p-value of Breslow-Day test for the hypothesis that all individual odds-ratios are equal

Source data: <DATASET> <DATE>

Program: <SAS PROGRAM> <DATE>

Table 14.3.3: PASI – PASI 75 responders – LOCF (FAS)
(Part 2 of 2)

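### The SAP's numeric rule for co-primary PASI 75 response lacks a minus sign: as printed, patients who are unchanged or up to 75% worse count as responders

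*SAP*

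**What the plan says.** SAP 3.4.6.2, under the primary efficacy endpoints, defines PASI 75 response at Week 12 as "75% improvement in PASI score compared to baseline (i.e. percent of change from baseline $\leq 75" per cent, with no minus sign.

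The scale is fixed elsewhere in the SAP:

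- Section 3.1: "Change from baseline = post baseline value – baseline value".
- Section 3.1: "Percent change from baseline = $100 * \text{change from baseline} / \text{baseline value".
- Section 3.2.1.1: "The PASI score ranges from 0 to 72, with a higher score indicating increased disease severity".

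Every other definition of the endpoint is in words only. SAP 3.2.1.4 has "75% improvement (response) in their PASI score (PASI 75) and", the footnote to Table 14.3.3 in the SAP appendix has "75% improvement in PASI score", and Table 1 and section 5.5.7 of the protocol are equally verbal. None gives a signed cut-off.

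PASI 50 has no numeric rule of its own: "The PASI 50 responder rate at Week 12 (Day 84) will be evaluated according to the primary efficacy endpoints". The time-to-PASI 50 and time-to-PASI 75 analyses have none either.

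**The concern.** The parenthesis is the only numeric statement of how a co-primary endpoint is derived, and it has the wrong sign for the scale the SAP defines. Programmed as printed, it would count as responders patients who improved a little, did not change, or worsened by up to 75%. Nearly every assessed patient in every arm would qualify.

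SAP 3.5.1 states that "missing PGA assessments and/or any parts of the PASI assessments will be evaluated as failure to achieve improvement". Under that rule the literal response rate would mostly record who had a Day 84 assessment. The CMH test and common odds ratio for PASI 75 would then say almost nothing about efficacy. The PASI 75 results at Weeks 4, 8 and 16 and the time to PASI 75 would be affected only if the same literal rule were reused there.

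**Working it through.** **Inputs.** Percent change is 100 × (post − baseline) / baseline (SAP 3.1). Higher PASI is worse (SAP 3.2.1.1). Baseline PASI is 10 to 20 (protocol 5.3.2, inclusion criterion 2a). The printed cut-off is ≤ 75% (SAP 3.4.6.2).

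**Step 1: can the printed cut-off be reproduced?** A 75% improvement means post = 0.25 × baseline. Substituting, 100 × (0.25 − 1) = −75. Three ways of expressing the same endpoint are:

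- signed percent change, as the SAP defines it: ≤ −75%;
- percent reduction, counted as positive: ≥ 75%;
- post-baseline value as a percentage of baseline: ≤ 25%.

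None gives ≤ 75%. On the percent-reduction scale, ≤ 75% would select the patients who improved least.

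**Step 2: Day 84 PASI needed to be a responder.** The printed rule gives post ≤ 1.75 × baseline; the consistent rule gives post ≤ 0.25 × baseline.

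| Baseline PASI | Printed rule (≤ 75%) | Consistent rule (≤ −75%) |
|---|---|---|
| 10 | ≤ 17.5 | ≤ 2.5 |
| 15 | ≤ 26.25 | ≤ 3.75 |
| 20 | ≤ 35 | ≤ 5 |

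This step uses only the documents. A patient with baseline 10 and Day 84 PASI of 15 (50% worse) responds under the printed rule.

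**Step 3: size among assessed patients.** The documents give no distribution of percent change. I assume a normal distribution with mean 0 to −50 and SD 30 to 40. With Φ the standard normal distribution function, the response rate is Φ((cut-off − mean)/SD).

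- Printed rule, lowest: mean 0, SD 40, Φ(1.875) = 96.96%. Highest: mean −50, SD 30, Φ(4.167) = 99.998%.
- Consistent rule, lowest: mean 0, SD 30, Φ(−2.5) = 0.62%. Highest: mean −50, SD 40, Φ(−0.625) = 26.60%.

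Percent change cannot fall below −100%. Truncating the same distributions there gives 96.94% to 99.998% (printed) and 0.58% to 17.93% (consistent).

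**Step 4: what happens to an arm difference.** Take two arms with SD 40 and means −10 and −50 before truncation.

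| Rule | Mean −10 | Mean −50 | Difference |
|---|---|---|---|
| Printed | 98.32% | 99.91% | 1.6 points |
| Consistent | 5.21% | 26.60% | 21.4 points |
| Consistent, truncated at −100% | 4.04% | 17.93% | 13.9 points |

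**Step 5: effect of missing data counted as failure.** SAP 2.2 plans 150 patients to obtain 120 evaluable, so 30/150 = 20% are not evaluable. If all 30 were in the FAS with no Day 84 assessment, the overall rate under the printed rule would be 0.80 × 97.0% = 77.6% up to 0.80 × 100% = 80%. This is an upper-end illustration, because evaluability can also be lost in other ways.

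**Step 6: sample size.** The SAP's figures (67.4% against 40%, two-sided 0.10, 80% power) return 40 per group with power 0.801. They are stated as response rates and do not depend on the cut-off's sign, so the correction leaves them alone.

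**The case against.** The strongest reply is that nobody could mistake the endpoint. The name PASI 75, the sentence containing the parenthesis, the variable list and the table footnote all say improvement, and the PGA rule in the next sentence runs in the right direction. A placebo response near 100% of assessed patients would also stand out against the 40% placebo example in SAP 2.2. The trial is exploratory and its p-values are descriptive. I accept that the intent is clear and that a literal error would probably be noticed. But it would be noticed after unblinding, and the SAP itself rests credibility on specifying the analysis beforehand.

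Second, the minus sign may have been lost when the PDF was converted to text. Minus signs survive in the SAP 3.1 formula and the flow chart, but these are not typeset like the inequality, and small symbols are lost elsewhere: SAP 3.4.5 lacks a leading # that the same formula carries under Table 14.3.1. This point stands, so the source page must be checked.

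Third, steps 3 to 5 rest on assumptions. With mean −50 and SD 40, about 10.6% of the untruncated distribution lies below −100%; after truncation the two means in step 4 become about −8.7 and −41.8. Patients can also leave the evaluable set for prohibited medication or low compliance while keeping Day 84 data. Moreover, the PASI 75 table shells are titled LOCF, against the failure rule in SAP 3.5.1; if LOCF were used, the rate would no longer mainly reflect attendance. These limits affect the illustrations, not the contradiction or the thresholds in step 2.

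Fourth, the wording for PASI 50 is not contradictory. That is right: a numeric rule there is a clarification, not a correction.

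**Conclusion.** The concern holds. As printed, the numeric definition of co-primary PASI 75 is inconsistent with the SAP's own percent-change formula and with the words it is meant to explain, and no other passage supplies a correct number. The threshold error, a factor of seven in Day 84 PASI (1.75 against 0.25 of baseline), follows from the documents alone. The response-rate ranges and arm differences depend on the assumed normal distribution, and the 77.6% to 80% figure on all 30 non-evaluable patients being FAS members without Day 84 data. The one reservation about the finding itself is that the sign may be present on the source page. Nothing here shows that the analysis was run wrongly. Because this is the operational rule for a co-primary endpoint and costs almost nothing to correct, it must be fixed.

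**What to change.** Check the source page of SAP 3.4.6.2. If the minus sign is absent, change the parenthesis to: percent change from baseline ≤ −75%. In the same section, state the PASI 50 rule as percent change from baseline ≤ −50%. Say that both rules apply at Weeks 4, 8, 12 and 16 and define the event in the time-to-PASI 50 and time-to-PASI 75 analyses.

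This is a short text correction to be made before unblinding. It has no operational cost and leaves the intended endpoint, the test and the sample size unchanged.
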